#### 5.4.1 Blood tests

All of the blood tests specified here are mandatory for routine medical care before, during, and after transcatheter mitral valve repair procedure. The results are recorded as research values and in surveillance for adverse events. **No other blood tests are reported as adverse events.**

The specific blood tests are enumerated below, and reported as study adverse events if change from baseline > 10% AND out-of-range:

| Test   | Detail  | Inpatient value to record | Timepoints to collect   |
|--|---|---------------------------|-------------------------|
| Blood count: hemoglobin                                  | Marker of anemia and hemodilution.  | Lowest                    | Baseline through 30d    |
| Blood count: hematocrit                                  | Marker of anemia and hemodilution.  | Lowest                    | Baseline through 30d    |
| Blood count: white blood cell count                      | Nonspecific marker of inflammation and infection.   | Highest                   | All except 6 mo         |
| Blood count: platelet                                    | Nonspecific marker of coagulation and of inflammation.                                    | Lowest                    | Baseline through 30d    |
| Chemistry: Albumin                                       | Marker of nutritional status and frailty  |                           | Baseline only           |
| Chemistry: Creatinine                                    | Marker of renal excretion.  | Highest                   | All                     |
| Chemistry: Estimated glomerular filtration rate (eGFR)   | Calculated from age, sex, race, and creatinine  | Lowest                    | All                     |
| Chemistry: NT-Pro-Brain natriuretic peptide (NT-Pro-BNP) | Marker of volume overload.  | Lowest                    | All                     |
| Chemistry: Cardiac troponin                              | Marker of cardiomyocyte injury, institution-specific subtype (Troponin-I or Troponin-T).  | Highest                   | Baseline through 30 day |
| Chemistry: Bilirubin, total                              | Used to classify Childs-Pugh status, collected only if available from clinical evaluation | Highest                   | Baseline only           |

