#### **10.0 ADVERSE EVENT REPORTING**

##### **10.1 DEFINITIONS**

*Adverse events:* Any untoward medical occurrence in a human subject, including any abnormal sign (e.g., abnormal physical exam or laboratory finding), symptom, or disease, temporally associated with the subject's participation in the research, whether or not considered related to the subject's participation in the research.

This will include:

- Expected events related to the subject's disease process during active enrollment in the research protocol and do not directly result from use of the investigational device or study.
- Procedural events directly related to the cardiac catheterization procedure and recovery from the procedure and do not directly result from use of the investigational device.

*Serious Adverse Event (SAE):* A serious adverse event that results in any of the following and NOT directly related to the device. This includes any event that

- Results in death
- Is life-threatening (places the subject at immediate risk of death from the event as it occurs);
- results in in-patient hospitalization or prolongation of existing hospitalization;
- results in a persistent or significant incapacity;
- results in a congenital anomaly/birth defect (not relevant to this study); or
- based upon appropriate medical judgment, may jeopardize the subject's health and may require medical or surgical intervention to prevent one of the other outcomes listed in this definition.

*Adverse Device Effect (ADE):* Any untoward or unintended response to a medical device. This definition includes any event resulting from insufficiencies or inadequacies in the instructions for use or the deployment of the device or any event that is a result of user error.

During this clinical investigation an event should be considered related to the device when it is the result of:

- Transcatheter Mitral Cerclage Annuloplasty procedure
- Transcatheter Mitral Cerclage Annuloplasty device

An event will be considered NOT related to the Transcatheter Mitral Cerclage Annuloplasty procedure when it is the result of a pre-existing medical condition.

*Anticipated Adverse Device Effects (AADEs):* An AADE is an adverse event with a reasonable possibility that the device or procedure caused or contributed to the event. The following AADEs are considered anticipated based on judgement and clinical experience:

- Death

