- Mechanical injury to the myocardium or heart valves that may cause elevation of myocardial biomarkers (Troponin) other than myocardial infarction
- Mechanical injury to, or decline in function of, tricuspid or aortic heart valves or subvalvular apparatus causing valve regurgitation including requiring mechanical intervention
- Chest pain
- Cardiogenic shock or hypotension caused by valvular, subvalvular, or myocardial injury during or after cerclage implantation procedure requiring vasopressor support or mechanical circulatory support or other mechanical or surgical intervention

- Myocardial erosion which may cause myocardial perforation, intracardiac shunt, pericardial effusion or tamponade and which may require surgical or transcatheter intervention
- Renal injury or failure, including contrast-induced nephropathy, requiring temporary or permanent hemodialysis or medical treatment
- Volume overload, congestive heart failure, dyspnea, pulmonary edema, or pleural or pericardial effusion from procedure-related volume perturbations
- Congestive heart failure, cardiomyopathy, cardiogenic shock, respiratory failure, BNP elevation
- Narrowing the mitral valve too much, causing a condition called mitral valve stenosis. This can result in lung congestion causing shortness of breath, similar to symptoms of leaky (regurgitant) mitral valve.
- Respiratory failure requiring oxygen or mechanical support or mechanical ventilation
- Endocarditis or endarteritis or sepsis related to the cerclage device
- Venous thrombosis or thromboembolism including deep vein thrombosis, and pulmonary thromboembolism
- Ecchymoses or gastric bleeding related to anti-platelet medications.
- Other infection related to access site or procedure including urinary or pulmonary or sepsis
- Pain including back pain and access site pain and generalized pain
- Low or high blood pressure values, or low or high heart rate values, whether related to anesthesia or not
- Abnormal blood cell tests including hemoglobin, hematocrit, platelets and white blood cells
- Abnormal blood chemistries including creatinine, troponin, and NT-pro-BNP
- Radiation injury including intractable skin injury
- Emergency cardiovascular surgery

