### **10.2.4 Adverse event reporting timeframes**

The tabular summaries are provided below to aid investigators and staff. Further detail is provided below

Reporting obligations of site Principal Investigator

| Submission or event   | Reporting Time Frame                           | Recipient |
|---|--|-----------|
| Deviations from the investigational plan (emergency)            | Immediately, but no later than 3 working days  | Sponsor   |
| Unanticipated Adverse Device Effects (UADE)                     | Immediately, but no later than 10 working days | Sponsor   |
| Serious Anticipated Adverse Device Effect (SADE)                | Within 3 working days                          | Sponsor   |
| Anticipated Adverse Device effect (ADE)                         | Within 7 working days                          | Sponsor   |
| Serious Adverse Events (SAE-not directly related to the device) | Within 5 working days                          | Sponsor   |
| Adverse Events (AE)   | Within 7 working days                          | Sponsor   |
| Death   | Immediately but within 3 working days          | Sponsor   |
| Serious Unanticipated Problems (UP)                             | Within 3 working days                          | Sponsor   |
| Unanticipated Problems, non-serious (UP)                        | Within 3 working days                          | Sponsor   |
| Protocol Deviations (PD), serious                               | Within 3 working days                          | Sponsor   |
| Protocol Deviations, non-serious (PD)                           | Within 7 working days                          | Sponsor   |
| Non-compliance, Serious   | Within 3 working days                          | Sponsor   |
| Non-compliance, Continuing                                      | Within 7 days                                  | Sponsor   |
| Non-compliance, Non-serious                                     | Within 7 days                                  | Sponsor   |

Reporting obligations of NIH Principal Investigator

| Submission or event   | Reporting Time Frame  | Regulatory Body  |
|---|---|------------------|
| Current Investigator list                                       | Every 6 months  | FDA              |
| IDE Progress Report or Continuing Review                        | Annual  | FDA; IRB         |
| Deviations from the investigational plan (emergency)            | Within 5 working days   | IRB; FDA         |

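### Section 5.4.1 records the lowest inpatient NT-proBNP, which is the favourable extreme, so a transient rise after the procedure can be missing from the case report form

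*Combined protocol and SAP*

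**What the plan says.** Section 5.4.1 of the combined protocol and SAP gives the blood tests two uses: "The results are recorded as research values and in surveillance for adverse events". Its table has a column for the inpatient value to record. In the row "Chemistry: NT-Pro-Brain natriuretic peptide (NT-Pro-BNP" the description is "Marker of volume overload", the inpatient value is *Lowest*, and collection is at all timepoints.

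The listed tests are to be "reported as study adverse events if change from baseline > 10% AND out-of-range". The sentence does not say whether this trigger applies to the one recorded inpatient value or to any inpatient result. It also states no direction.

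Section 10.1 fixes the harmful direction. Its list of anticipated adverse device effects includes "Congestive heart failure, cardiomyopathy, cardiogenic shock, respiratory failure, BNP elevation" and, as a separate item, "Abnormal blood chemistries including creatinine, troponin, and NT-pro-BNP".

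**The concern.** NT-proBNP is harmful when it rises, on the protocol's own description, yet the table keeps the smallest inpatient value. With repeat samples, a value near or below baseline displaces the peak, and the recorded field shows no rise. That conflicts with the surveillance use the section states.

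Two things could be at stake: the accuracy of the inpatient laboratory field, and the adverse-event count if sites apply the trigger only to the recorded value. Inpatient volume overload is one of the events section 10.1 anticipates from the procedure, so this is a period in which the value should be informative.

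**Working it through.** **1. Row-by-row reading of the 5.4.1 table.** Eight tests are collected after baseline and have an inpatient entry.

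| Test | Recorded extreme | Harmful extreme recorded? |
|---|---|---|
| Hemoglobin, hematocrit, platelets, eGFR | Lowest | Yes |
| White cells, creatinine, troponin | Highest | Yes |
| NT-proBNP | Lowest | No |

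Bilirubin also has an entry (*Highest*) but is collected at baseline only. Counting it gives eight of nine rows; NT-proBNP is the only exception either way. Section 10.1 groups NT-proBNP with creatinine and troponin as abnormal chemistries, and both of those are recorded as *Highest*. No other section asks for the peak NT-proBNP or explains the choice.

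**2. Illustration (assumed values).** Baseline 2000; inpatient 2100, 4000, 1900 pg/mL. The lowest is 1900: (1900 − 2000)/2000 = −5%, trigger not met. The highest is 4000: +100%, trigger met if out of range.

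**3. Two readings of the trigger.** Reading A: it applies to the recorded value only. Reading B: any inpatient result can trigger, worsening only. On B the choice of extreme cannot change reporting, because some sample exceeds 1.1 × baseline exactly when the highest does.

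**4. Size under reading A.** The plan gives no figure to reproduce. Assumptions, because the documents supply none of these: within-person CV 25% (range 15–35%), log-normal values, independent errors, one baseline value, k inpatient samples, subject already above range.

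σ = √ln(1 + CV²), which is 0.246 at CV 25%. Let m_j be the true level of sample j relative to baseline, and φ and Φ the standard normal density and distribution function. The chance of a recorded rise above 10% is

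- Lowest: ∫ φ(z) ∏_j [1 − Φ((ln 1.1 + σz − ln m_j)/σ)] dz
- Highest: 1 − ∫ φ(z) ∏_j Φ((ln 1.1 + σz − ln m_j)/σ) dz

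Results at CV 25%, with the range over CV 15–35% in brackets:

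| Scenario | k | Lowest | Highest |
|---|---|---|---|
| One sample doubled, others at baseline | 2 | 39% (33–41) | 96% (91–100) |
| | 4 | 16% (12–18) | 96% (92–100) |
| One doubled, others at 1.5 × baseline | 2 | 80% (70–93) | 98% (94–100) |
| | 4 | 63% (51–84) | 99% (97–100) |
| All doubled | 2 | 92% (82–100) | 99% (96–100) |
| | 4 | 87% (73–99) | 100% (99–100) |
| Stable (chance reports) | 2 | 23% (18–26) | 55% (47–58) |
| | 4 | 12% (8–14) | 70% (62–73) |

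With k = 1 the two columns are identical.

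The 39% in the first row is not real detection. A single stable sample exceeds baseline by more than 10% with probability 1 − Φ(ln 1.1/(σ√2)) = 1 − Φ(0.0953/0.348) = 0.39. Under *Lowest*, the undoubled sample decides almost everything.

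If the trigger has no direction, chance reports under *Lowest* on reading A are 77% (63–83) with two samples and 81% (69–86) with four, mostly from falls.

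**5. As a research value.** In a stable subject the median of lowest/true is exp(σ Φ⁻¹(1 − 0.5^(1/k))): 0.874 for k = 2 and 0.782 for k = 4, that is 13% and 22% below the true level. The highest is 14% and 28% above. Neither extreme is unbiased.

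**The case against.** Several points against the concern stand.

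- **Repeat samples are not required.** The schedule in section 5.4 marks blood tests once under Inpatient, and no section asks for serial NT-proBNP. With one sample there is no effect.
- **Reading B may be what was meant.** The trigger sentence is about the tests, not the recorded value, and section 10.2.3 likewise speaks of tests that are monitored. Reporting is then unaffected, and every detection contrast above belongs to reading A.
- **Other routes exist.** A recognised elevation is an anticipated adverse device effect. Section 10.2.4 requires the site to report an "Anticipated Adverse Device effect (ADE") to the sponsor within seven working days. Source documents go to the sponsor (13.5), and all source data are to be verified (14.2.4).
- **The model inputs are assumed**, and *Highest* produces more chance reports on one reading.
- ***Lowest* may be a deliberate research value**, since research is one of the two stated uses.

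None of this removes the inconsistency. Verification compares the form with source, so a correctly copied lowest value agrees and need not expose a missing peak. The separate listing depends on the site recognising the rise and does not correct the laboratory field. A research reason for *Lowest* is nowhere stated, and it would not serve the surveillance use. The form itself is not in the documents, but the protocol column sets what it should hold.

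**Conclusion.** The concern holds and is minor. As written, the plan records the favourable extreme for one test only, against its own statement of which direction is harmful. That conclusion rests on the text alone; its effect requires only that more than one inpatient sample is drawn.

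How much is lost depends on assumptions. On reading A a brief, fully resolved doubling is largely missed, a partly resolved one is missed in 20% (two samples) to 37% (four) at CV 25%, and a sustained one is mostly caught. On reading B only the recorded value is wrong. No endpoint in sections 9.3 to 9.5 and no stopping rule in section 9.9 uses NT-proBNP, so trial conclusions on those are untouched.

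The missing direction in the trigger is a lesser point. Section 10.1 defines an adverse event as "Any untoward medical occurrence in a human subject", and section 10.2.3 speaks of baseline conditions that become more severe. Both already point to worsening only; section 5.4.1 should say so.

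**What to change.** - In the 5.4.1 table and the case report form, change the NT-proBNP inpatient value from *Lowest* to *Highest*. If *Lowest* was intended as a research value, state the reason and keep it as a second, labelled field.
- Recover peaks from source records for treated subjects with more than one inpatient sample.
- As a clarification, word the trigger so that the change of more than 10% must be away from the normal range as well as ending out of range. With *Highest* and a worsening-only trigger, readings A and B give the same NT-proBNP reports, so sites cannot diverge on that point.

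The cost is one table cell, one form field, one sentence and a limited source look-back. The downside is chance reports in stable subjects who are already above range. At CV 25% these become 55% with two samples and 70% with four. That is a rise from 23% and 12% if sites now use reading A with worsening only, a fall from 77% and 81% if they use reading A without direction, and no change on reading B with worsening only. The excess comes from the 10% threshold and is not a reason to record the favourable extreme for one test.

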## **5.5 CMS CLINICAL TRIAL POLICY (CTP) ON FINANCIAL COVERAGE OF ROUTINE MEDICAL COSTS OF CARE IN THIS RESEARCH PROTOCOL.**

By virtue of NHLBI sponsorship of clinical research protocols, enrolling sites qualify for Centers for Medicare and Medicaid Services (CMS) coverage of associated routine costs of medical care under the CMS Clinical Trial Policy (CTP). This policy is detailed at <https://www.cms.gov/Medicare/Coverage/ClinicalTrialPolicies/index.html>. According to this policy, CMS is “explicitly authorize[d to provide] payment for routine patient care costs...and costs due to medical complications associated with participation in clinical trials...

“Routine costs of a clinical trial include all items and services that are otherwise generally available to Medicare beneficiaries (i.e., there exists a benefit category, it is not statutorily excluded, and there is not a national non-coverage decision) that are provided in either the experimental or the control arms of a clinical trial except the investigational item...”

Site billing and reimbursement offices are reminded not to use the IDE number, but instead only bill for routine services using the NCT number, which is mandatory. Moreover, site billing and reimbursement offices are reminded that under the CTP pathway, the trial is not listed on any CMS web site.

## **6.0 ELIGIBILITY ASSESSMENT**

Eligibility criteria were revised in Amendment F to allow patients with symptomatic heart failure (HFrEF and HFpEF) accompanied by mitral valve regurgitation. The original criteria are retained below (with text struck-out) to allow readers, regulators, and reviewers the opportunity to understand the selection conditions for all subjects.

### **6.1 REVISED SELECTION CRITERIA BEGINNING WITH AMENDMENT F**

#### **6.1.1 Inclusion Criteria**

1. Adults age  $\geq 21$  years
2. Symptomatic functional mitral valve regurgitation
  - a. Mild or greater mitral valve regurgitation, LVEF  $\leq 0.50$ , and NYHA class III - IV heart failure
  - b. Moderate or greater mitral valve regurgitation and NYHA II - IV heart failure, irrespective of LV systolic function
3. On optimal medical therapy for at least one month (see section 6.3)
4. Left ventricular ejection fraction  $\geq 0.20$  assessed by echocardiography, CT, or CMR
5. Suitable coronary venous anatomy for Transcatheter Mitral Cerclage Annuloplasty based on pre-procedural cardiac CT or coronary venogram
6. Concordance of the Study Eligibility Committee
7. If present, a MitraClip was implanted at least 30 days previously

#### **6.1.2 Exclusion criteria**

1. Subjects unable to consent to participate
2. Subjects unwilling to participate or unwilling to return for study follow-up activities.
3. Prior cardiac implanted electronic devices (CIED) likely to be entrapped by cerclage.
  - o Candidates with coronary sinus or left ventricular pacing or defibrillation leads that are not likely to be entrapped by cerclage, evident on baseline CT or angiogram, are eligible to participate.
4. TAVR within 6 weeks

5. Intended concurrent structural heart procedure, such as aortic or tricuspid valve intervention
6. Aortic stenosis more than mild in severity
7. Single-leaflet *MitraClip* detachment, if present
8. Pregnancy or intent to become pregnant prior to completion of all protocol follow-up procedures

## 6.2 ORIGINAL SELECTION CRITERIA BEFORE AMENDMENT F

### 6.2.1 ~~Inclusion Criteria~~

8. Adults age  $\geq 21$  years
9. Severe functional mitral valve regurgitation defined as:
  - a. Effective orifice area  $\geq 20\text{mm}^2$ , AND
  - b. Regurgitant volume  $\geq 30\text{mL/beat}$
10. On optimal medical therapy for at least one month (see section 0)
11. NYHA class II, III or IV heart failure symptoms
12. Left ventricular ejection fraction  $\geq 0.20$  assessed by echocardiography, CT, or CMR
13. Suitable coronary venous anatomy for Transcatheter Mitral Cerclage Annuloplasty based on pre-procedural cardiac CT or coronary venogram
14. Concordance of the Study Eligibility Committee

#### *ADDITIONAL INCLUSION FOR MITRACLIP ARM*

15. Predominantly functional mitral regurgitation as indication for *MitraClip*
16. At least 30 days after *MitraClip* implantation, and at least 24 months after *MitraClip* implantation if enrolled in COAPT trial

### 6.2.2 ~~Exclusion criteria~~

9. Subjects unable to consent to participate
10. Subjects unwilling to participate or unwilling to return for study follow-up activities.
11. TAVR within 6 weeks
12. Prior cardiac implanted electronic devices (CIED) likely to be entrapped by cerclage: Cardiac Resynchronization Therapy (CRT) with coronary sinus lead; Implantable Cardioverter Defibrillator (ICD) with lead likely to be entrapped based on corelab assessment of baseline CT; or, Single- or dual-chamber pacemaker with lead likely to be entrapped based on corelab assessment of baseline CT
13. Prior Cardiac Resynchronization Therapy (CRT) with biventricular pacemaker/Implantable Cardioverter Defibrillator (ICD) and coronary sinus lead
14. Intended concurrent structural heart procedure, such as aortic or tricuspid valve intervention
15. Aortic stenosis more than mild in severity
16. Pregnancy or intent to become pregnant prior to completion of all protocol follow-up procedures

#### *ADDITIONAL EXCLUSION FOR MITRACLIP ARM*

17. Single-leaflet detachment of *MitraClip*

### **6.3 RATIONALE FOR SELECTION CRITERIA**

The protocol originally selected subjects with severe mitral regurgitation defined according to European Society of Cardiology guidelines , which define the intended treatment population. Beginning with Amendment F, eligibility was extended to patients with severe symptomatic cardiomyopathy (NYHA Class III or IV) and any ( $\geq$ mild) functional mitral valve regurgitation based on evidence in the first ten subjects of significant functional and symptomatic benefit out of proportion to reduction in mitral valve regurgitation. At the time of the amendment, no subjects had been enrolled with MitraClip and >24 months had elapse since enrollment completed in the COAPT trial, so enrollment of subjects having MitraClip implants was consolidated into a single treatment arm. “Optimal medical therapy” refers to guideline-directed medical therapy according to contemporary ACC/AHA/HFSA  and/or ESC  guidelines. This includes pharmacotherapy of atherosclerosis with medications such as antiplatelet medications, lipid-lowering agents, anti-ischemic medications, and revascularization therapy as indicated. This also includes Guideline-Directed therapy for symptomatic left ventricular dysfunction and mitral valve regurgitation as tolerated including beta-adrenergic blockade, angiotensin converting enzyme or angiotensin receptor blocker or angiotensin receptor-neprilysin inhibitor, diuretics, and additional agents as indicated and as tolerated including aldosterone antagonists, hydralazine-nitrate, and cardiac electronic implanted device therapy. “Optimal medical therapy” is confirmed by the Study Eligibility Committee.

The selection criteria allow enrollment of the intended population with little anticipated selection bias. Planned concurrent valve procedures such as TAVR are disallowed. Subjects having pre-existing implanted devices that might be disturbed or damaged by the cerclage procedure or implant tension are disallowed from this early feasibility study (EFS). Conversely, when demonstrated by imaging that CIED follow the “outer curvature” of the coronary sinus allowing an “inner curvature” cerclage implant, such candidates are allowed to participate in the trial beginning with Amendment F.

Children are excluded because this is an early feasibility study. Pregnant women are excluded because of the research radiation.

The inclusive selection criteria and geographic extent of enrolling sites are expected to allow recruitment of a diverse economic, ethnic, and racial mix of patients that reflects the incident disease. Specifically, the results are expected to be generalizable to Medicare and Medicaid beneficiaries because of age and disease-related disability.

The Study Eligibility Committee confirms eligibility before enrollment (see section 13.8).

